Study Protocol with Statistical Analysis Plan

Title:

Evaluation of IL-2, IL-5, and IL-17 Levels in the Saliva of Patients Treated with Stainless Steel Crowns

NCT Number: NCT06439095

Date: May 1,2025

This prospective before-and-after clinical study was approved by the Local Ethics Committee of Van Yüzüncü Yıl University in accordance with the Declaration of Helsinki (Approval No: 2024/01-03). The study protocol was registered on ClinicalTrials.gov (NCT06439095). All parents/guardians were informed about the procedures and potential outcomes and were asked to sign a written informed consent form prior to participation. Children whose parents declined consent were excluded from the study.

Selection of Participants

Participants were selected among 30 patients who applied to the Pediatric Dentistry Clinic of Van Yüzüncü Yıl University Faculty of Dentistry. The study was conducted on 20 observations from 10 pediatric patients undergoing general anesthesia. Data were collected at two time points: baseline (before treatment) and seven days after treatment. All treatment plans followed routine pediatric dental protocols, and no modifications were made for study purposes. Therefore, the study posed no harm to the patients.

Inclusion criteria:

- Children aged 3–10 years
- Voluntary participation
- Clinical indication for stainless steel crowns (SSC) without need for additional crowns in the next month
- Adequate unstimulated saliva volume in the morning
- No need for space maintainers in the following month
- Candidates for treatment under general anesthesia

Exclusion criteria:

- History of previous dental treatment
- History of systemic disease or syndromes
- History of allergic reactions
- History of using imitation jewelry
- Presence of metal restorations or orthodontic appliances
- Patients not undergoing general anesthesia

This was a pilot/exploratory study, and no formal sample size calculation was performed. As no previous studies were available evaluating IL-2, IL-5, and IL-17 gene expression after SSC placement, the primary aim was to obtain preliminary data and provide a basis for future large-scale research.

Study Design

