The study was performed under general anesthesia in children with material loss requiring SSC treatment. Patients were selected among those needing at least four posterior SSCs. To avoid delays and ensure no new SSC needs arose during the study period, all treatments were completed in a single session following standard pediatric protocols. Of 30 children evaluated, 12 met inclusion criteria and were enrolled.

Only patients receiving SSC or SSC combined with composite restorations were included. Those receiving other metal restorations, such as amalgam or space maintainers, were excluded.

Dental Treatments

The proximal surfaces of the teeth planned for SSCs were contoured with a #69L round bur on a high-speed handpiece. Occlusal surfaces were reduced by ~1 mm. Caries removal was performed using a round bur on a low-speed handpiece. In case of pulp exposure, an access cavity was prepared with an 008 fissure bur, and appropriate pulp therapy was conducted. SSCs (Kids Crown, Shinhung, Korea) were selected and cemented with nickel- and chromium-free glass ionomer cement (Meron, Voco, Germany).

Saliva Sampling

Saliva samples were collected at two time points: before treatment (control) and seven days after treatment. Parents were advised to follow a low-nickel diet and avoid nickel-containing materials until saliva collection was completed. The diet excluded canned foods, acidic foods cooked in stainless steel, herring, oysters, asparagus, beans, mushrooms, onions, corn, spinach, tomatoes, peas, whole grain flour, pears, rhubarb, tea, cocoa, chocolate, and baking powder. The use of fluoride-containing mouth rinses was also prohibited. Approximately 5 mL of unstimulated saliva was collected into polyethylene tubes free of nickel/chromium, washed with acetone and distilled water. Saliva was collected in the morning before surgery and at follow-up, without prior rinsing.

Clinical Examination

At follow-up, a pediatric dentist examined the oral mucosa and soft tissues for signs of allergic reactions, inflammation, or tissue changes using a dental mirror and light. Parents and children were asked about any discomfort or changes over the previous seven days.

RNA Isolation

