Tissue samples were carefully collected with a sterile spatula, weighed at 25 mg, and placed in RNase-free tubes with 700 μ L TRIzol reagent. Samples were homogenized, incubated at room temperature for 5 minutes, mixed with chloroform, and centrifuged at 12,000 \times g, 4°C for 15 minutes. The upper phase was transferred, mixed with isopropanol, incubated, and centrifuged. The RNA pellet was washed with 75% ethanol, centrifuged, and air-dried. Pellets were dissolved in RNase-free water or buffer.

cDNA Synthesis

cDNA synthesis was performed on a cold plate at +4°C using the All-in-One cDNA synthesis kit (Solver). 1 μ L of RNA (10 ng/ μ L) was used in a 20 μ L reaction, incubated at 42°C for 60 minutes and 80°C for 10 minutes.

Gene Expression Analysis

cDNA products were analyzed using RotorGene Q. β -actin was used as the reference gene, and primers were designed for IL-2, IL-5, and IL-17. The PCR mixture included 12 μ L SYBR Green qPCR Master Mix, 2 μ L forward primer, 2 μ L reverse primer, 5 μ L water, and 4 μ L cDNA

(total volume 25 μ L). PCR cycling conditions were: 95°C for 15 min, followed by 45 cycles of 95°C for 30 s and 60°C for 30 s.

Statistical Analysis Plan

CT values obtained from Real-Time PCR were normalized using the Bio-Q online bioinformatics tool. Gene expression levels were calculated using the $2^{-\Delta\Delta CT}$ method. Group differences were analyzed using one-way ANOVA, and the Tukey HSD post-hoc test was used to identify significant differences. ΔCT values were calculated by subtracting housekeeping gene CT values from target gene CT values, and expression differences between groups were visualized using bar graphs.

Key Results Summary

Patients included were aged 3–6 years. Of the 12 enrolled, two were excluded due to loss to follow-up, leaving six girls and four boys. IL-2, IL-5, and IL-17 gene expression changes were assessed. Control group expression levels were low and homogeneous; follow-up samples showed marked increases, particularly in IL-5 and IL-17. IL-2 expression increased slightly without statistical significance. IL-5 increased moderately and reached statistical significance ($p < 0.05$), while IL-17 showed a sixfold increase and the highest variability, also reaching statistical significance. Heatmap and Venn diagram analyses illustrated expression changes and potential interactions among the genes.

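### With two time points Tukey HSD corrects nothing, and the three interleukins get separate significance verdicts with no primary gene and no adjustment across genes

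*Combined protocol and SAP*

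**What the plan says.** The Statistical Analysis Plan section names one inferential procedure: "Group differences were analyzed using one-way ANOVA, and the Tukey HSD post-hoc test was used to identify significant differences". It does not define the groups, set a significance level, name a primary gene or mention any adjustment across genes.

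The groups have to be inferred from the design. Selection of Participants says "Data were collected at two time points: baseline (before treatment) and seven days after treatment" and "The study was conducted on 20 observations from 10 pediatric patients undergoing general anesthesia". Saliva Sampling makes the baseline sample the control: "Saliva samples were collected at two time points: before treatment (control) and seven days after treatment". There is no separate control arm.

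Key Results Summary then gives one verdict per gene. For IL-2: "IL-2 expression increased slightly without statistical significance". For IL-5: "IL-5 increased moderately and reached statistical significance", with p < 0.05 and no exact value. IL-17 is also called significant, with no p-value, and is described as the most variable. Selection of Participants calls the study pilot or exploratory.

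**The concern.** A post-hoc multiple-comparison test suggests that multiplicity has been dealt with. On the design described it has not. Tukey HSD adjusts for the number of pairwise group comparisons, and two time points give only one. The multiplicity that exists runs across the three genes, and nothing in the plan addresses it.

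What is at stake is which genes may be called significant. The study aims to supply a basis for larger research, so these labels may decide which interleukins are taken forward. With one p-value given only as a bound and another not given, a reader cannot check whether either claim would survive an adjustment.

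**Working it through.** The plan states no family-wise error rate, power or sample size calculation, so there is no figure of its own to reproduce.

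**Inputs.** From the documents: two time points, 10 children, 20 observations, three genes. Inferred: a 0.05 level per gene, because Key Results Summary prints it for IL-5; applying it to IL-2 and IL-17 is an assumption. Not given, so varied: the between-gene correlation r (all three genes share the β-actin reference, which could make them positively correlated) and the within-child correlation w between baseline and day 7. Simulations used normal data and 100,000 trials per setting.

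**1. Tukey with two groups.** Unpaired degrees of freedom are 20 − 2 = 18. The Tukey critical value on the t scale is q(0.95; 2, 18)/√2 = 2.1009. The t-test value is t(0.975; 18) = 2.1009, and √F(0.95; 1, 18) = 2.1009. At t = 2.3 the studentized-range p and the t-test p are both 0.0336. Tukey adds nothing.

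**2. Three valid tests at 0.05.** If independent, 1 − (1 − 0.05)³ = 1 − 0.857375 = 14.3%. The upper bound is 3 × 0.05 = 15%. For paired t-tests on 10 pairs (9 df):

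| r | any p < 0.05 | with Holm |
|---|---|---|
| 0 | 14.3% | 4.9% |
| 0.3 | 13.8% | 4.8% |
| 0.5 | 12.9% | 4.6% |
| 0.7 | 11.3% | 4.1% |

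Without adjustment, the rate is about 8.8% at r = 0.9 and 5.0% at r = 1.

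**3. The unpaired ANOVA as named, on paired data.** The variance of the mean change is 2σ²(1 − w)/n, but the ANOVA uses 2σ²/n. Its standard error is therefore too large by a factor 1/√(1 − w): 1.20 at w = 0.3 and 1.41 at w = 0.5. With independent genes:

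| w | per gene | any of three |
|---|---|---|
| 0 | 5.0% | 14.1% |
| 0.3 | 2.3% | 6.6% |
| 0.5 | 0.9% | 2.8% |
| 0.7 | 0.2% | 0.6% |

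The same inflated standard error lowers power.

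**4. The alternative grouping: control, IL-2, IL-5, IL-17.** Tukey then covers six pairs, three of them control versus gene. With 10 independent values per group (36 df), the chance of any false control-versus-gene result is about 3% with equal SDs, 3.2% with SDs 0.5/1/1/2, 4.1% with 0.2/1/1.5/3 and 4.5% with 0.3/0.5/1/2. These SDs are illustrative; the documents give none. In the last case nearly all the error falls on IL-17 (about 4.5%), with about 0.06% on IL-5 and 0% on IL-2. The pooled variance is dominated by IL-17, so the IL-2 and IL-5 tests become very insensitive.

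**5. Effect on the reported verdicts.** The Holm steps are 0.05/3 = 0.0167, 0.05/2 = 0.025 and 0.05. With IL-2 not significant, IL-5 and IL-17 hold the two smallest p-values. Both survive only if the smaller is at most 0.0167 and the larger at most 0.025. An IL-5 p-value between 0.025 and 0.05 meets the printed criterion but fails Holm.

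**The case against.** A reader might infer that the actual chance of a false significant gene here is 13–14% when 5% was promised. The documents do not support that. The figure belongs to tests with a true 5% size and low to moderate between-gene correlation. The named ANOVA, if run unpaired, has that size only near zero within-child correlation, and its family-wise rate can be below 5%. Nor is a family-wise 5% promised: the plan sets no level.

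A reader might also infer that no interpretation of the groups controls the error. That is wrong as well. With the four groups in step 4, Tukey roughly held the error for the control-versus-gene contrasts in the cases tried. The cost of that reading is insensitivity for IL-2 and IL-5.

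Finally, the study is openly exploratory, and three unadjusted p-values are acceptable in such a study if presented as descriptive. This stands, and it limits the seriousness of the point. It does not remove it, because the summary sorts the genes into significant and not significant. A low error rate produced by ignoring the pairing is one flaw offsetting another, not planned control.

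**Conclusion.** The point holds in a limited form. On the design described, Tukey HSD is redundant, and nothing adjusts across three genes that each receive a verdict. The nominal family-wise error is up to about 14% for three valid tests at an inferred 0.05, and lower if the genes are strongly correlated. For the unpaired ANOVA as written, the rate cannot be stated without the within-child correlation; over the values tried, from 0 to 0.7, it ran from about 14% to 0.6% with independent genes. Under the four-group reading the error is roughly held, but pooling weakens the IL-2 and IL-5 tests, so a null result for IL-2 says little.

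It cannot be concluded that the IL-5 or IL-17 finding is false. The documents do not give the p-values needed to tell whether either survives adjustment.

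**What to change.** Delete the ANOVA and Tukey sentence. In its place, specify one paired test of baseline versus day 7 for each gene on the ΔCT scale, each gene with its own variance. Report the three exact raw p-values and the three Holm-adjusted p-values. Then choose one of two courses and state it: base the significance wording in Key Results Summary on the Holm-adjusted values, or label all three p-values exploratory and descriptive and remove the significance wording.

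The cost is a short change to the plan, a re-run on existing data and an edit to the summary. The downside is that IL-5 may lose its significant label. Because the results are already known, the change should be recorded as made after the data were seen.

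### The planned ANOVA and bar graphs cannot show whether the sixfold IL-17 rise is general or confined to some of the ten children; individual paired changes should be reported

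*Combined protocol and SAP*

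**What the plan says.** - **Design.** Under Selection of Participants: "The study was conducted on 20 observations from 10 pediatric patients undergoing general anesthesia". Under Saliva Sampling: "Saliva samples were collected at two time points: before treatment (control) and seven days after treatment". The two groups are therefore the same ten children at two times.
- **Analysis.** Under Statistical Analysis Plan: "Group differences were analyzed using one-way ANOVA, and the Tukey HSD post-hoc test was used to identify significant differences". The section mentions both 2^-ΔΔCT and ΔCT and does not say which one enters the ANOVA.
- **Display.** The same section says "expression differences between groups were visualized using bar graphs". It plans no other figure, and no summary of change within a child.
- **Result.** Under Key Results Summary: "IL-17 showed a sixfold increase and the highest variability, also reaching statistical significance". No SD, interval, exact p value or number of children who rose accompanies this. The summary also mentions a heatmap and a Venn diagram but does not say whether either shows individual children.
- **Status.** Under Selection of Participants: "This was a pilot/exploratory study, and no formal sample size calculation was performed". The stated purpose is to supply preliminary data for larger research.

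**The concern.** A group mean, its bar and its F test depend on the data only through means and variances. With ten children, very different sets of individual changes can share both. A gene reported as significant and also as the most variable of the three is where this matters most: the variability may be uneven size in a rise that every child shows, or a strong rise in some children and none in the rest.

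The two readings lead to different follow-on studies. A general rise supports a mean-change endpoint sized on the spread of that change. A subset rise calls for looking at who responds, and a sample size based on the mean could mislead. Since the pilot exists to inform a larger study, its output should let the reader see which reading the data favour.

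**Working it through.** **What can be reproduced.** Only the counts: 12 − 2 = 10, 6 + 4 = 10, 10 × 2 = 20. All agree with "Of the 12 enrolled, two were excluded due to loss to follow-up, leaving six girls and four boys" and with the stated number of observations. The sixfold result cannot be reproduced, because no SD or individual values are given.

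**Assumptions for the example.** These are mine, not the plan's: control fold = 1 in all ten children with negligible spread (the results summary describes controls as low and homogeneous); sixfold is an arithmetic mean fold; the test is a two-group one-way ANOVA on fold, α = 0.05.

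**Pattern A: k children rise equally, the rest do not change.**
- Riser's fold = (60 − (10 − k))/k = 1 + 50/k.
- Follow-up variance s² = (50/k)² × k(10 − k)/90.
- With control variance 0, F = 5² × 10/s² = 250/s² = 9k/(10 − k), on 1 and 18 df.

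| k | Riser's fold | s | F | ANOVA p | Paired t p (9 df) |
|---|---|---|---|---|---|
| 2 | 26.0 | 10.54 | 2.25 | 0.151 | 0.168 |
| 3 | 17.67 | 8.05 | 3.86 | 0.065 | 0.081 |
| 4 | 13.5 | 6.45 | 6.00 | 0.025 | 0.037 |
| 5 | 11.0 | 5.27 | 9.00 | 0.008 | 0.015 |

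Four is the smallest k that is significant here, and the median child is then unchanged (fold 1). A sixfold mean stays significant up to s = 5 × √10/2.101 = 7.5.

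**Pattern B: every child rises.** Take folds 2, 2, 2, 3, 3, 4, 5, 6, 10, 23.
- Sum 60, mean 6.
- Squared deviations: 3×16 + 2×9 + 4 + 1 + 0 + 16 + 289 = 376; s² = 376/9 = 41.8; s = 6.46.
- F = 250/41.8 = 5.98, p = 0.025.

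Pattern A (k = 4) and pattern B give practically the same bar, SD and p value. In A six children do not change; in B all ten at least double.

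**The same two patterns as within-child change in ΔCT**, in cycles, signed so that a rise is positive, with t(0.975, 9 df) = 2.262:
- A: log2(13.5) = 3.755. Mean = 4 × 3.755/10 = 1.502, SD 1.939, SE 0.613. CI 1.502 ± 1.387 cycles, which is 2.8-fold (1.1 to 7.4). Median 0, range 0 to 3.75 cycles.
- B: mean 2.092, SD 1.146, SE 0.362. CI 2.092 ± 0.820 cycles, which is 4.3-fold (2.4 to 7.5). Median 1.79, range 1.00 to 4.52 cycles.
- Leave-one-child-out geometric mean fold: A 2.4 to 3.2, B 3.5 to 4.6. This guards against a single dominant child; it is the plot, median and range that separate A from B.

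**Sensitivity.**
- *Noise.* With four risers, child SD 0.5 and sample SD 0.5 cycle, about 63% of simulated studies reach p < 0.05 on the fold scale. With sample SD 1 cycle this falls to about 27% (child SD 0.5) or 16% (child SD 1). The documents give no SD, so none of these is preferred.
- *Scale.* If sixfold is a geometric mean, four risers would each need 6^(10/4) = 88-fold.
- *Number of groups.* If Tukey pooled four or six gene-by-time groups, with assumed SDs for the others, three risers give p = 0.019 to 0.064 and four give 0.002 to 0.018.

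**Would counting risers settle it?** With symmetric noise, an unchanged child appears to rise half the time. With four clear risers the expected count is 4 + 6 × 0.5 = 7 of 10. The chance of at least 6 is P(Bin(6, 0.5) ≥ 2) = 1 − 7/64 = 89%. Counting only rises above one cycle, at least 6 of 10 still occurs in about 7% of simulations at sample SD 0.5 and about 42% at sample SD 1. The exact 95% CI for 4/10 is 12% to 74%.

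**The case against.** **The problem is mainly one of scale and pairing.** This largely stands as to size. As paired ΔCT, the four-child pattern is 2.8-fold rather than sixfold, so a paired ΔCT analysis removes most of the striking example. It does not remove the ambiguity: patterns A and B then give overlapping intervals (1.1 to 7.4 and 2.4 to 7.5), and neither interval says how many children changed.

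**The heatmap may show individual samples.** This stands as a limit. A reader might infer that the study displays nothing but group means; the documents do not support that, because the heatmap is undescribed. It lies outside the Statistical Analysis Plan section, however, and nothing says it is per child or paired.

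**Nobody claims that every child responded.** Correct. The summary discloses high variability and the study is labelled exploratory. Its general statement that follow-up samples showed marked increases can be read as a general response, but it does not assert one.

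**Allergy gives no support.** One might argue that the study looks for allergic reactions, which affect some children only. The follow-up dentist "examined the oral mucosa and soft tissues for signs of allergic reactions, inflammation, or tissue changes", but the plan does not link that check to cytokine change, and children with a history of allergic reactions are excluded. The point does not rest on this argument.

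**Ten children with one sample each side cannot be classified as responders.** This stands, and it rules out a decision rule based on counts.

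**Conclusion.** The point holds as a reporting gap. For ten children measured twice, the planned ANOVA and bar graphs cannot separate a general IL-17 rise from a subset rise; with the same sixfold mean and p = 0.025, either six children or none may be unchanged. The figure of four risers rests on an arithmetic mean fold, equal rises, little noise and a two-group ANOVA on fold. With more noise four would often not reach significance, and with pooled groups three might.

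A reader might go further and infer that four children drove the reported IL-17 result. The documents do not support that: they give no individual data, and high variability is equally consistent with an uneven rise in every child. The gap is worth closing because the pilot is meant to inform a larger study and the change costs almost nothing.

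**What to change.** 1. Replace the bar graphs with a before/after line plot of each child's ΔCT, one panel per gene.
2. For each gene, report the median and range of within-child ΔΔCT and the leave-one-child-out range of the mean change, alongside a paired analysis of ΔCT with its 95% CI.
3. State the scale on which the sixfold figure was averaged, and whether the heatmap shows individual children.
4. Optionally add the number of ten children who rose, and who rose by more than one cycle, with exact 95% CIs, labelled as descriptive only.
5. Do not call a rise general merely because most children rose, and do not describe it as general unless the individual plots support that.

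**Cost:** re-plotting and a few summaries from data already held; no new samples. **Downside:** the headline may read less favourably.

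### All reported results come from the 10 of 12 enrolled children who completed follow-up, with no check on how the two lost children (17%) could alter them

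*Combined protocol and SAP*

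**What the plan says.** Study Design gives the intake: "Of 30 children evaluated, 12 met inclusion criteria and were enrolled". The Key Results Summary gives the attrition: "Of the 12 enrolled, two were excluded due to loss to follow-up, leaving six girls and four boys". Selection of Participants gives the analysed data: "The study was conducted on 20 observations from 10 pediatric patients undergoing general anesthesia".

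On timing, Selection of Participants states: "Data were collected at two time points: baseline (before treatment) and seven days after treatment". Saliva Sampling adds: "Saliva was collected in the morning before surgery and at follow-up, without prior rinsing". Study Design says that "all treatments were completed in a single session following standard pediatric protocols".

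The comparison in the Statistical Analysis Plan reads: "Group differences were analyzed using one-way ANOVA, and the Tukey HSD post-hoc test was used to identify significant differences". That section defines no analysis set, no rule for missing values and no sensitivity analysis. The documents do not say when or why the two children were lost, and they do not compare them with the completers at baseline.

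The only numerical effect reported is for IL-17: "IL-17 showed a sixfold increase and the highest variability, also reaching statistical significance". IL-5 is given as significant at the 5% level, without an exact p-value or a fold change.

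**The concern.** Two children are one sixth of this cohort. The day-7 visit is also when the mucosa is examined and families are asked about discomfort, so coming back may be related to how the child's mouth felt. If so, the missing responses need not resemble the observed ones. The bias could run either way, because a family with a symptomatic child might be more or less likely to return.

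The stated analysis does not require the two children to be dropped. A one-way ANOVA treats the two time points as separate groups, so it could have taken any baseline values that exist for them.

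The study's stated purpose is to supply preliminary data for larger research. With the SD held fixed, a later study sized on a mean log2 change of 5/6 of the reported one (both lost children unchanged) would need (6/5)² = 1.44 times as many children. Sized on 7/6 of it (both lost children at twice the observed log2 change), it would need (6/7)² = 0.73 times as many. A reader planning that study has no way to see this range.

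**Working it through.** **1. The plan's own counts.** Enrolled 12 (Study Design), excluded 2 (Key Results Summary): 12 − 2 = 10 = 6 girls + 4 boys. 10 × 2 time points = 20 observations, matching Selection of Participants. So the lost children contribute nothing at either time. The loss is 2/12 = 16.7% (exact 95% interval about 2% to 48%).

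**2. Sensitivity of the IL-17 figure.** The sixfold value comes from the Key Results Summary. The fold change f of each lost child is an assumption, and the documents do not say which kind of mean sixfold is.

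- Geometric: fold over 12 = 2^[(10 × log2 6 + 2 × log2 f)/12], with log2 6 = 2.585.
- Arithmetic: fold over 12 = (10 × 6 + 2f)/12.

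| Assumed f for both lost children | Geometric | Arithmetic |
|---|---|---|
| 1/6 | 3.3 | 5.0 |
| 0.5 (one cycle down) | 4.0 | 5.1 |
| 1 (no change) | 4.5 | 5.2 |
| 6 (same as completers) | 6.0 | 6.0 |
| 36 (twice the log2 change) | 8.1 | 11.0 |

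On the log2 scale, f = 1 and f = 36 lie equally far below and above the completers' mean (0 and 5.17 around 2.585), so they form a symmetric pair.

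**3. Effect of the two baselines alone.** Suppose the 2^−ΔΔCT calibrator is the baseline group mean, which is not stated, and the lost children's baseline ΔCT differed from the completers' mean by one cycle. The 12-child baseline mean then moves by 2/12 = 0.17 cycle, and sixfold becomes 6 × 2^(∓0.17), about 5.3 or 6.7.

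**4. Precision gained from 12 baselines and 10 follow-ups.** Let s1 and s2 be the baseline and follow-up SDs of ΔCT and ρ the within-child correlation.

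- Variance of the mean change from 10 pairs: (s1² + s2² − 2ρ·s1·s2)/10.
- Saving from two extra baselines: (s1 − ρ·s2)² × (1/10 − 1/12).
- With s1 = s2, the proportional saving reduces to (1 − ρ)/12. The variance ratios are 0.917 (ρ = 0), 0.942 (0.3), 0.958 (0.5) and 0.975 (0.7).
- With s2 = 2·s1, as an assumption, the ratios are 0.967 (ρ = 0), 0.993 (0.3) and 1.000 (0.5).

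So for ρ of zero or more and equal variances, the gain is at most about 8% of the variance, or about 4% of the standard error. It can be nothing.

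**5. Sensitivity of significance.** This is an illustration with a paired t-test on within-child changes, not the plan's own test. Take 10 changes with mean m and SD = m√10/t, where t gives the stated p on 9 df. Add two changes of c·m and recompute on 11 df.

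| p with 10 children | c = 0 (no change) | c = −1 (opposite change) |
|---|---|---|
| 0.049 | 0.051 | 0.15 |
| 0.04 | 0.042 | 0.13 |
| 0.01 | 0.012 | 0.075 |
| 0.001 | 0.002 | 0.038 |

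**The case against.** The strongest reply is that this is a declared pilot with no planned sample size. It discloses the step from 12 to 10 and claims a direction and significance rather than a precise fold. Under no change in both lost children, IL-17 is still more than fourfold up and most p-values barely move. This stands, and it limits the size of the point.

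Three further objections also stand. First, the documents call the 12 children enrolled. That all were treated and gave a baseline sample is inferred from the phrase loss to follow-up and the pre-surgery sampling. No storage is described, and RNA Isolation refers to weighed tissue rather than saliva, so it is not certain what material could be assayed. Second, a child with a baseline only carries no information on its own change. A mixed model assumes that loss is random given the observed data, so it cannot test or repair loss that depends on the day-7 response. Third, any value given to the missing children is an assumption. A single zero-change row would show one direction of a bias whose direction is unknown.

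A reader might infer that the reported increases are inflated, or that available data on treated children were discarded. The documents support neither. They give no reason for the losses, and they do not say that samples from these children were kept.

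**Conclusion.** The point holds as a gap in the analysis, of moderate size. All results rest on 10 completers out of 12 enrolled, and nothing shows how far the two missing children could alter them. Under symmetric assumptions the IL-17 figure ranges from about 4.5-fold to 8.1-fold if sixfold is a geometric mean. If it is an arithmetic mean, no change lowers it to about 5.2-fold.

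The direction of the IL-17 increase is unlikely to change. With no change in both lost children, significance is lost only if p was already very near 0.05; losing it from a clearly smaller p needs changes in the opposite direction. Exact p-values for IL-5 and IL-17 are not given, so a reader cannot place them on this scale. That baseline values exist for the lost children is probable but not documented.

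**What to change.** 1. Replace the one-way ANOVA with a mixed model on ΔCT for each gene (time fixed, child random), using every available baseline and the 10 follow-ups. The main benefit is that it respects the pairing within children, which the ANOVA ignores; the extra baselines add little. If no further baselines can be used, the model in practice gives the paired analysis of the 10 completers. State that it does not correct outcome-dependent loss.
2. Label all fold changes and p-values as completer-based, and state when and why the two children were lost.
3. Show the two children's baseline ΔCT beside the completers', if available.
4. Add a two-sided bounding row per gene, presented as an assumption: both lost children unchanged, and both at twice the completers' mean log2 change. State whether each fold is a geometric or an arithmetic mean.

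The cost is a short re-analysis and a wider stated range. If the two baselines were kept but not run, there is also their assay: 2 children × 4 genes = 8 wells in single replicate, plus RNA isolation, cDNA synthesis, controls and a possible between-run effect. If no sample was kept, items 2 and 4 need no laboratory work.
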